7.4. DEFINITIONS

Study groups: The group/cohort that originally received passive treatment during the RCT will be referred to as the passive-active group. The group/cohort that originally received active tvCVS treatment during the RCT will be referred to as the active-active group.

Study day: The study day will be calculated in reference to the date of the first baseline virtual visit during the RCT (Day 0). Although the informed consent for the OLE will be completed on day 113, plus or minus window days, because the RCT and OLE are part of the same protocol and the evaluation of effectiveness in the OLE depends on RCT data, all dates in this OLE SAP will be in reference to the first RCT visit (Day 0) as is specified in the protocol.

Analysis day: The analysis day will be calculated in reference to the date of the last assessment in RCT/first assessment in OLE (Day 113). Analysis day will be utilized for comparisons for passive-active participants.

OLE Baseline value: Values obtained at the End of Treatment (EOT) visit for the RCT will define the OLE baseline values. Values obtained at the most recent visit during the RCT will define the OLE baseline values in cases where data is missing for the EOT visit for the RCT.

Adherence (%): Adherence is defined as the total number of times subjects used the device in a given treatment period divided by twice the number of days the subject participated in that treatment period, multiplied by 100 to give a percentage.

Duration of Follow-up: The duration of follow-up will be defined as the number of days from the OLE Baseline until the End of Treatment period 2 (day 365) assessment or the last completed visit (phone call, virtual or in clinic).

Adverse Event:

Per protocol, an AE is any untoward medical occurrence, unintended disease or injury, or untoward clinical signs (including abnormal laboratory findings) in participants, users, or other persons, whether or not related to the investigational medical device. This definition includes events related to the investigational medical device and the events related to the procedures involved. For purposes of analyses, any AE specified on the Adverse Events eCRF page is considered an AE.

Adverse Device Effect (ADE):

Per protocol, an ADE is an AE related to the use of an investigational medical device. For purposes of analysis, any AE specified on the Adverse Events eCRF page that is possibly related, probably related, or related to the study device will be considered an ADE.

Serious Adverse Event (SAE):

Per protocol, a SAE is an AE that has

- Led to death,
- Led to serious deterioration in the health of the participant, that either resulted in:
 - 1. A life-threatening illness or injury, or
 - 2. A permanent impairment of a body structure or a body function, or
 - 3. In-patient or prolonged hospitalization, or

4. Medical or surgical intervention to prevent life-threatening illness or injury or permanent impairment to a body structure or body function.

• Led to fetal distress, fetal death or congenital abnormality or birth defect.

For analysis purposes, SAEs are AEs which are defined as serious on the Adverse Events eCRF.

Serious Adverse Device Effect (SADE):

Per protocol, a SADE is an ADE that has resulted in any of the consequences characteristic of a serious adverse event. For analysis purposes, any AE on the Adverse Events eCRF page that is possibly related, probably related, or related to the study device and is noted as serious will be considered a SADE.

Unexpected Adverse Device Effect (UADE):

Per protocol, a UADE is an SADE on health or safety or any life-threatening problem or death caused by, or associated with, a device, if that effect problem, or death was not previously identified in nature, severity, or degree of incidence in the investigational plan or application (including a supplementary plan or application), or any other unanticipated serious problem associated with a device that relates to the rights, safety, or welfare of participants. For analysis purposes, any event noted on the SADE/UADE Report eCRF page that is noted as a UADE will be considered a UADE.

SADEs and UADEs are AEs specified as such on the eCRF. More information on SAEs, ADEs, SADEs, and UADEs can be found in Protocol (Version 6.0: 02 Apr 2024) Section 8.2.

7.5. ANALYSIS OF STUDY CONDUCT

Descriptive statistics for the participants will be described for the ITT, mITT, and PP populations. Study treatment administration, duration of follow-up, discontinuation from study treatment and the reasons for discontinuation will be summarized. Coded protocol deviations and protocol violations will also be summarized as follows:

- Major/Important versus Minor versus No Impact, where:
 - Major/Important are protocol deviations that might significantly impact completeness, accuracy, and/or reliability of study data OR could significantly affect a participant's rights, safety or well-being
 - Minor are protocol deviations with minor impact on data quality or patient safety
 - No impact are protocol deviations that do not impact data quality or patient safety

7.6. DESCRIPTION OF THE DATASET USED FOR ANALYSIS

SAS-compatible and csv data sets will be exported directly from the iMediData RAVE Electronic Data Capture (EDC) platform. Exceptions may include data for the MDS-UPDRS Part III that has been re-scored by central blinded raters within the Machine Medicine Kelvin-PD platform, data related to Finger-tapping tests and Timed Up and Go tests captured with the Mon4t EncephaLog, treatment adherence data downloaded from the returned study Devices, a file that defines types of medications taken to address motor and nonmotor symptoms of PD including the levodopa equivalent daily dose for each participant, and a file that defines all the assignment of each consented participant into populations for analysis (e.g., ITT, mITT and PP) and reasons for exclusion and withdrawal where appropriate. Data for these exceptions will be provided as csv files created with Microsoft Excel.

7.7. PARTICIPANT DISPOSITION

Numbers of early withdrawals during the OLE will be reported descriptively overall and by treatment period, and categorized reasons provided for early withdrawal will be reported. Withdrawals due to similar adverse events will be grouped into categories.

7.7.1. Demographics and Baseline Characteristics

The following baseline characteristics at both the RCT baseline and the OLE baseline will be summarized for all participants for each analysis population (i.e., ITT, mITT and PP): age, sex, years since PD diagnosis, levodopa equivalent daily dose (LEDD) at start of treatment ⁶, race and ethnicity.

Disease characteristics and motor phenotypes (i.e., tremor-dominant, postural instability gait difficulty or intermediate), postural instability and gait difficulty (PIGD) and Hoehn & Yahr scores will be reported and defined using methodology defined within the RCT (Appendix 1).

Comparability of baseline characteristics will be assessed. Here, these characteristics will be compared between the start of the RCT (during which time they would receive the passive

treatment) and the start of the OLE (during which time they will receive the active treatment). The characteristics will include disease characteristics, concomitant medications and outcome scores as these items may have changed over the course of the RCT. Descriptive statistics will be presented by corresponding timing of assessment (i.e., RCT Baseline or OLE Baseline). Differences in scores will be determined using a paired t-test or Wilcoxon Signed test for continuous variables and a McNemar's test for binary variables. Characteristics will be considered different in circumstances where p < 0.05. If baselines prove to be significantly different ($\alpha = 0.05$), adjustments to corresponding efficacy analyses will be made by incorporating baseline level as a covariate.

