7.8.2. Primary Endpoint and Comparison of Interest

The primary endpoint is the change in MDS-NMS total score at the end of treatment. The primary comparison is its change in MDS-NMS total score during the RCT treatment period (days 29-113) versus the change in MDS-NMS total score during the OLE treatment period 1 (days 113-197). This analysis of the primary comparison will only utilize the passive-active treatment group. The analysis will utilize data obtained during the RCT as well as data obtained from the OLE baseline and the twelve weeks of the OLE in which the participants will have been given the intervention.

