7.7.1. Primary Endpoint

The primary endpoint is the change in MDS-NMS total score at the end of the treatment period (day 113) relative to baseline (mean of day 0 and day 29) scores.

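### The OLE baseline check tests the passive-period response itself and, when significant, adjusts for it, which moves the primary contrast towards the device if passive participants improved

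*SAP*

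**What the plan says.** - **OLE SAP 7.4 (Definitions):** "Values obtained at the End of Treatment (EOT) visit for the RCT will define the OLE baseline values". For the passive-active group this is the score after 12 weeks of passive treatment.
- **OLE SAP 7.7.1:** "these characteristics will be compared between the start of the RCT" and the start of the OLE, within the same people. Outcome scores are explicitly covered: "The characteristics will include disease characteristics, concomitant medications and outcome scores as these items may have changed over the course of the RCT". The test is paired: "Differences in scores will be determined using a paired t-test or Wilcoxon Signed test for continuous variables". The threshold follows: "Characteristics will be considered different in circumstances where p < 0.05". The consequence is that "adjustments to corresponding efficacy analyses will be made by incorporating baseline level as a covariate".
- **OLE SAP 7.8.2:** the primary comparison, in the passive-active group only, is the "change in MDS-NMS total score during the RCT treatment period (days 29-113) versus the change" during OLE treatment period 1 (days 113-197). Section 7.8.2.1 states a null of equal change in the two periods and tests it one-tailed at 0.05.
- **OLE SAP 7.8:** the model comes from RCT SAP 7.7, with subject nested within ARM. RCT SAP 7.7 has its own rule that adds a baseline effect when baseline scores differ significantly between arms.
- **RCT SAP 7.7.1:** the RCT endpoint is measured "relative to baseline (mean of day 0 and day 29) scores", not from day 29 alone.

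**The concern.** In a randomised comparison, a baseline check looks at two groups before treatment. Here there is one group, and its second baseline is measured after passive treatment. For an outcome score, OLE baseline minus RCT baseline is the passive-period change. A significant result therefore does not show imbalance; it shows that the comparator period produced a response. The plan then uses that result to decide whether the comparator's own end-point score enters the model as a covariate.

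At stake are the OLE primary endpoint and the hierarchical secondary endpoints that have a baseline score. OLE SAP 2.1 says these results are meant to support reimbursement and clinical adoption.

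**Working it through.** **Inputs from the plan.** n=74 in the passive-active group (OLE SAP 4); MDS-NMS SD 70.8 and estimated MCID range 32.7 to 35.4 points (RCT SAP 4); one-tailed alpha 0.05 (OLE SAP 7.8.2.1); two-sided trigger at 0.05 (OLE SAP 7.7.1).

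**Assumptions, not in the documents.** Visit-to-visit correlation (0.5 to 0.8) and size of the passive response. Baseline level is read as each period's own baseline.

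**Step 1: the plan's own figure.** OLE SAP 4 gives power above 98% for a difference of 2.64, SD 5.32, n=74. The standardised effect is 2.64/5.32 = 0.496, and 0.496 x √74 = 4.27. The paired t-test then has 98.8% power two-sided, which reproduces the figure. The trigger is the same kind of test: a passive-period change of 2.64 with SD 5.32 would set off the rule 98.8% of the time.

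**Step 2: identity.** Let B1 = RCT baseline and B2 = OLE baseline = day 113 score. Then D_passive = day 113 - B1 = B2 - B1. The paired t statistic for B2 against B1 equals the one-sample t statistic for D_passive (both -1.682 on a simulated data set). This is exact when the check and the endpoint use the same RCT baseline.

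**Step 3: effect of the covariate.** With change = a + t x ARM + b x (period baseline), the adjusted contrast is

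D_active - D_passive - b x (B2 - B1) = D_active - (1 + b) x D_passive.

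Regression to the mean makes b negative. Under the null D_active = D_passive = D, the contrast is -b x D instead of 0, so it has the sign of D.

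**Step 4: chance of triggering, worked once.** With correlation 0.7 and a single baseline visit, the SD of change is 70.8 x √(2 x 0.3) = 54.8 and its standard error is 54.8/√74 = 6.4. A 20-point change is 20/6.4 = 3.1 standard errors, so the rule triggers in nearly nine trials in ten (88% simulated).

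**Step 5: simulation under the null, subject-nested model.** RCT baseline as the mean of two visits, equal correlations, 3,000 trials per row. The slope b was about -0.43, -0.29 and -0.16 at correlation 0.5, 0.65 and 0.8.

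| Change in each period | Correlation | Rule triggers | Mean estimate under rule | One-sided error, no rule | With rule |
|---|---|---|---|---|---|
| -10 | 0.5 / 0.65 / 0.8 | 29 / 38 / 59% | -2.0 / -1.8 / -1.2 | 9.8 / 9.7 / 8.7% | 9.8 / 9.8 / 8.9% |
| -20 | 0.5 / 0.65 / 0.8 | 80 / 91 / 99% | -7.6 / -5.6 / -3.1 | 8.4 / 9.8 / 9.3% | 17.8 / 19.1 / 16.2% |
| -32.7 | 0.5 / 0.65 / 0.8 | 99.6 / 100 / 100% | -14.2 / -9.3 / -5.2 | 9.9 / 9.0 / 9.5% | 41.3 / 31.0 / 22.7% |

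The unadjusted paired test had 4.4-5.7% error throughout.

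**Step 6: separating the rule from the nesting.** Three visits (days 29, 113, 197), correlation 0.6-0.8, equal or serially decaying, 20-point improvement in both periods:

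- The rule triggers in about 78-97% of trials; the shift is about 2-7 points towards the device.
- Paired covariance: error goes from about 4-5% to 7-15%. The upper part of that range needs serial correlation.
- Subject-nested model: error goes from about 5-9% to 12-18%.

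A shortcut of (1 - correlation) x passive change is too large for the paired model with equal correlations. At correlation 0.7 it gives 0.3 x 20 = 6 points; the simulated shift is 3.4.

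**Step 7: other directions.** With +20 in both periods (worsening) and correlation 0.65, the Step 5 model gives a mean estimate of +5.6, against the device, and error falls from 10.0% to 2.5%. With a 20-point passive improvement and no further change in the OLE, the adjusted contrast is still about +14 against the device (unadjusted +20).

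**The case against.** **The covariate is not defined.** OLE SAP 7.7.1 says only baseline level. If each participant's RCT baseline were entered for both periods, it would cancel and the contrast would not move. This stands as a condition on the result. The period-specific reading is the natural one, because OLE SAP 7.8.4.1 measures change from the corresponding baseline, but that phrase defines the change score and not the covariate.

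**Adjusting for a lower starting score can be defended** on floor effects or regression to the mean. That supports a pre-specified sensitivity analysis. It does not support a primary model selected by a significance test of the comparator's own response.

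**A reader might infer more than the documents support:**

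- *That the rule always favours the device.* It does so only if passive participants improve; if they worsen, it works against the device.
- *That it can produce a positive result by itself.* It does not turn a plateau in the OLE into a benefit (Step 7).
- *That the whole 12-18% error is due to the rule.* The nesting in OLE SAP 7.8 already gives about 5-9%.
- *That small passive responses matter.* At 10 points, error is essentially unchanged.
- *That every gated secondary is affected.* The overall CGI-I is a change rating with no baseline score, so the rule cannot act on it.

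**Scale.** A shift of 2-7 points is about 6% (2/35.4) to 21% (7/32.7) of the estimated MCID, in an open-label single-group comparison. That limits the consequence but does not make the test valid.

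**Conclusion.** The concern holds as a fault in a stated rule. That the outcome-score check is a test of the passive-period change follows from OLE SAP 7.4, 7.7.1 and 7.8.2. That the adjustment biases the contrast depends on reading baseline level as each period's own baseline. On that reading, an improvement under passive treatment is partly credited to the device, and the analysis no longer addresses the null in 7.8.2.1.

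The size rests on an assumed correlation and passive response. The 20-point case in Step 6, with its 2-7 point shift and roughly 7-15% error under paired covariance, is the fair summary of the rule's own effect. The scope is the OLE primary endpoint and the gated secondaries with a baseline score.

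**What to change.** 1. In OLE SAP 7.7.1, delete the significance-triggered adjustment for outcome scores. Keep the comparison of RCT and OLE baselines as description only.
2. In OLE SAP 7.8, state that the baseline-covariate rule imported from RCT SAP 7.7 does not apply to the within-participant OLE contrast. Otherwise the same trigger stays in force.
3. Make the primary OLE test the unadjusted within-participant contrast, OLE-period change minus passive-period change, with within-participant covariance. Day 113 is then an outcome and never a covariate.
4. State one RCT baseline, reconciling days 29-113 in OLE SAP 7.8.2 with the mean of days 0 and 29 in RCT SAP 7.7.1. Use each endpoint's own scheduled days. Do not use raw interim MDS-UPDRS Part III scores, because Protocol 4.1.1 specifies a modified exam at the virtual visits.
5. If an analysis adjusted for starting level is wanted, pre-specify it as a sensitivity analysis and define the covariate.

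The cost is SAP wording and model code. No data collection changes. The estimate may be less favourable to the device.

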7.7.2. Pre-study and Concomitant Medications

Within a group, the number and percentage of participants on concomitant therapies at RCT baseline and at the start of the OLE will be reported categorically using categories defined in section 7.6.3 of the SAP v6.0 for RCT Study (ID: SNS-PD-002).

Changes in medications to treat symptoms associated with PD during the RCT or the first 12-week treatment period of the OLE are protocol deviations. As such, changes in these medications would exclude participants from the PP analysis. Changes in medications in the mITT and the ITT populations will be summarized descriptively.

Certain concomitant medications (e.g., antihistamines or acetylcholinesterase inhibitors) may alter treatment efficacy by affecting neurotransmitter systems involved in the mechanisms of action for tvCVS. Subgroup analyses will be performed to compare treatment effects in study participants taking these concomitant medications during the trial.

7.7.3. Study Device Administration

Treatment adherence will be analyzed for the OLE. Treatment adherence data will be reported descriptively. Treatment adherence $\geq 70\%$ during the first 12-week treatment period in the OLE will be required for inclusion in the PP analysis (see section 7.2).

7.8. EFFICACY ANALYSIS

⁷Analysis of continuous endpoints will be conducted utilizing the methodology as described in section 7.7 of the SAP v6.0 for RCT Study (Appendix 1). For comparisons within the passive-active arm, the visit variable will be based on the adjusted analysis visit for the active comparisons and the subject effect of the model will be nested within ARM to account for the crossover nature of these data. For efficacy endpoints that have a baseline defined, only participants who have baseline data collected for the endpoints will be included in efficacy analyses.

7.8.1. Primary Objectives:

The primary objective is to further evaluate the effectiveness of TNM[™] Device treatments to reduce non-motor symptom burden in PD for the purposes of supporting reimbursement and clinical adoption.

7.8.2. Primary Endpoint and Comparison of Interest

The primary endpoint is the change in MDS-NMS total score at the end of treatment. The primary comparison is its change in MDS-NMS total score during the RCT treatment period (days 29-113) versus the change in MDS-NMS total score during the OLE treatment period 1 (days 113-197). This analysis of the primary comparison will only utilize the passive-active treatment group. The analysis will utilize data obtained during the RCT as well as data obtained from the OLE baseline and the twelve weeks of the OLE in which the participants will have been given the intervention.

7.8.2.1. Statistical Significance

The null hypothesis is that 12 weeks of active tvCVS treatments during the OLE will yield an equivalent change in the passive-active treatment group of NMS burden as that which occurred in response to passive treatment during the RCT. The alternative hypothesis is that the passive-active treatment group will demonstrate a greater reduction of NMS burden after 12 weeks of active tvCVS treatment during the OLE than occurred after 12 weeks of passive treatment during the RCT. Rejection of the null hypothesis will indicate that the intervention was successful. The threshold to determine statistical significance will be set at $\alpha = 0.05$ based upon a 1-tailed test.

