 - MDS-UPDRS Part II
 - GDS
 - PAS
 - PDSS-2
 - ESS
 - FACIT-F
 - ii. In clinic visit (day 113 +/- 3 days)
 - Concomitant medication and adverse event review
 - MDS-UPDRS Part III with video (captured using the Machine Medicine Kelvin software). *The timing of the administration of the MDS-UPDRS Part III from last DRT dose should be recorded and*

Clinician version – not for patient use

kept consistent with the timing from last dose to administration as noted in the BL2 visit. Administration must occur within 30 – 90 minutes after last dose.

- Mini-BESTest
- 10m TUG (Encephalog™)
- MDS-UPDRS Part I
- MDS-NMS (includes the NMF subscale)
- CGI-I (overall and focused)
- S&E
- Ear exam
- MoCA v8.3
- UPDRS I
- UPDRS IV
- PRO-PD
- Zarit Burden Interview
- Device Usability Questionnaire
- Conduct weight measurement
- Device return and supply return

After the completion of study assessments, participants will be offered the opportunity to consent to the OLE of the study. Participants will not be made aware of their allocation during the RCT portion of the study at any point. Used Devices will be promptly shipped back to the distributor using the Device Return form.

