7. STATISTICAL METHODS

7.1. GENERAL METHODS

Descriptive statistical methods will be used to summarize the data from this study, with formal hypothesis testing performed for the primary and key secondary efficacy endpoints. Unless stated

otherwise, the term "descriptive statistics" refers to number of participants, mean, median, standard deviation, minimum, and maximum for continuous data, and frequencies and percentages for categorical data. For categorical variables, the denominator of percentages will be the number of subjects in the treatment group, except for those collected by study visit and/or scheduled time point, in which case the denominator of percentages will be the number of subjects with a non-missing value at the visit and/or the scheduled time point.

All data collected during the study will be included in data listings. Unless otherwise noted, the data will be sorted first by RCT treatment group, subject number, and then by date within each subject number.

All statistical testing will be two-sided and will be performed using a significance (alpha) level of 0.05 unless otherwise specified. P-values will be presented to three decimal places. For exploratory endpoints, inferential analyses including 95% confidence intervals and p-values will be provided, and no statements about statistical significance will be made. The p-values will be provided as informational only.

The statistical analyses may be conducted with the SAS® software package version 9.4 or higher or with GraphPad Prism software version 9.3.1 or higher.

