7.8.2.2. Clinical Significance

Clinical significance is defined by how a treatment affects the extent to which a subject is currently living independent of help from others OR that there is a real genuine, palpable, and noticeable effect on daily life or how a patient feels, functions, or survives. Importantly, as the scores from the MDS-NMS are derived from the product of the symptom frequency (how often the patient has experienced a given non-motor symptom since the last evaluation with higher scores indicating more frequent experience) and symptom severity (impact of that symptom on how the patient has felt and functioned with higher scores indicating greater distress or disturbance to patient or caregiver), reductions in MDS-NMS total scores are inherently clinically meaningful in that they indicate improvements in how the participant is feeling and functioning. Given the inherent clinical meaningfulness of the MDS-NMS total score, the primary endpoint will be considered clinically meaningful, and therefore, successful, if there are statistically significant reductions in MDS-NMS total scores after active tvCVS treatment during the OLE relative to the change in response to the 12 weeks of passive treatment during the RCT.

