7.8.4. Secondary Endpoints

Multiplicity of study endpoints will be adjusted for using a hierarchical strategy whereby endpoints in the study are only considered to be statistically significant if both of the following are true: 1) p < 0.05 AND 2) the preceding endpoint was found to be statistically significant at the significance level $\alpha = 0.05$. More specifically, the hierarchical order for evaluation of efficacy endpoints is the following:

- 1. MDS-NMS Total Score (primary endpoint);
- 2. Combined measure of MDS-UPDRS Parts I, II, and III (sum score)
- 3. MDS-UPDRS Part II (secondary endpoint);
- 4. Overall CGI-I (secondary endpoint);
- 5. MDS-UPDRS Part III (secondary endpoint);
- 6. PDQ-39SI (secondary endpoint).

Note that all secondary endpoints have an *a priori* direction, thus, one-tailed tests will be utilized for analyses.

Secondary endpoint analysis will be conducted using the passive-active treatment group for the primary comparison of interest.

Analyses of the secondary endpoints will be conducted in a manner consistent with the primary endpoint except where noted.

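### The OLE plan calls the intervention successful from a fixed-order, blinded-passive-then-open-active comparison within one group, which cannot separate the device from period and open-label effects

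*SAP*

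**What the plan says.** OLE SAP 7.8.2 sets the change during RCT treatment (days 29-113) against the change during OLE treatment period 1 (days 113-197). It limits the test to one randomised group: "This analysis of the primary comparison will only utilize the passive-active treatment group". Section 7.8.4 does the same for the secondary endpoints: "Secondary endpoint analysis will be conducted using the passive-active treatment group for the primary comparison of interest".

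The general rule in 7.1 is two-sided testing at 0.05 unless otherwise specified. Section 7.8.2.1 does specify otherwise: the threshold is 0.05 "based upon a 1-tailed test". Its conclusion is: "Rejection of the null hypothesis will indicate that the intervention was successful". Section 7.8.2.2 adds that, given a statistically significant result, "the primary endpoint will be considered clinically meaningful, and therefore, successful".

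Section 2 describes the OLE as single-arm and open label, and Protocol 4.1 gives all OLE participants active treatment. The active-active group is defined in OLE SAP 7.4 and has the same OLE visits (Protocol Appendix 1.2), but no efficacy comparison in this SAP uses it. On masking of the earlier allocation, Protocol 4.1.1 says: "Participants will not be made aware of their allocation during the RCT portion of the study at any point".

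**The concern.** Every passive-active participant has passive treatment first, double-blind, and active treatment second, openly. Three things change at day 113: the device output, the period, and what participant and rater know about current treatment. A difference between the two changes is the sum of all three, and the test cannot say which one produced it.

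This is a practical worry here. The MDS-NMS is completed by a rater (Protocol 3.1.2) and scored from symptom frequency and severity. Blinded central rating is specified only for the in-clinic MDS-UPDRS Part III (Protocol 11). At consent, participants are told that the OLE provides the treatment found most effective (Protocol 6.1), so expectation may rise when treatment switches. In the other direction, regression after the non-motor entry threshold (Protocol 5.1) or an early response to passive treatment would enlarge the first-period improvement and could hide a real device effect.

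The first OLE objective in Protocol 1.1.2 is to show that the RCT result is reproduced, with reimbursement as the purpose. A non-device shift could pass as reproduction, or a real effect could be missed.

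**Working it through.** **Inputs from the documents.** OLE SAP 4: n = 74, difference 2.64 and SD 5.32 on MDS-UPDRS Part I, alpha 0.05, paired t-test. OLE SAP 7.8.2.1: one-sided 0.05. RCT SAP 4: MDS-NMS SD 70.8.

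**Assumptions, not in the documents.** The size of any non-device shift; an equal correlation of 0.6 to 0.8 between any two MDS-NMS visits; 74 active-active participants by the same attrition.

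**1. The plan's own figure.** 184 × 0.9 / 2 = 82.8 (83 stated) and 83 × 0.9 = 74.7 (74 stated). SE = 5.32/√74 = 0.618, noncentrality = 2.64/0.618 = 4.27, df 73. Power is 98.8% two-sided and 99.5% one-sided, so the stated figure of more than 98% reproduces.

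**2. What the model can separate.** The contrast is device effect + period effect + open-label effect, seen in one group in one order. Nesting subject within ARM (OLE SAP 7.8) handles within-person correlation. The conditional baseline covariate (7.7.1) handles differing starting levels. Neither identifies the three parts.

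**3. False success on the plan's paired inputs.** With no device effect and a favourable shift s, the chance of rejection is that a noncentral t (df 73, noncentrality s/0.618) exceeds 1.666.

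| Shift (Part I points) | Chance of success |
|---|---|
| 0 | 5% |
| 0.5 | 19.9% |
| 1.0 | 48.3% |
| 2.64 | 99.5% |

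An observed mean difference of 1.666 × 0.618 = 1.03 points is enough to reject. RCT SAP 4 uses 5.32 as a within-group SD. The SD of the difference between two changes is 5.32 × √(2(1 − r)), which equals 5.32 only at r = 0.5. At r = 0 it is 7.52 and a 1-point shift gives 30.4%; at r = −0.5 it is 9.21 and gives 23.6%.

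**4. The same on the MDS-NMS.** The contrast is Y197 − 2·Y113 + Y29, with variance 6σ²(1 − ρ). SE = 70.8 × √(6(1 − ρ))/√74, and the chance of rejection is P(Z > 1.645 − shift/SE).

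| ρ | SE | 5 points | 10 points | 15 points |
|---|---|---|---|---|
| 0.6 | 12.75 | 10.5% | 19.5% | 32.0% |
| 0.7 | 11.04 | 11.7% | 23.0% | 38.7% |
| 0.8 | 9.02 | 13.8% | 29.6% | 50.7% |

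With the two-visit mean baseline of RCT SAP 7.7.1, the factor 6 becomes 5.5 and the ranges are 11-14%, 20-31% and 34-54%.

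**5. Passive-active minus active-active over days 113-197.** On the Part I inputs with 74 per group, SE = 5.32 × √(2/74) = 0.875. If a shift is shared by both groups and there is no device effect, 20,000 simulated trials gave one-sided error of 5.3%, 4.8% and 4.8% at shifts of 0, 1 and 2.64. Power for 2.64 with no further gain in active-active is 91% one-sided (85% two-sided). A further active-active gain of 25% leaves 2.64 × 0.75 = 1.98 and 73% one-sided power; a gain of 50% leaves 1.32 and 44%.

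**The case against.** The strongest reply is that this SAP is openly limited to the passive-active group through day 197 (OLE SAP 1), the OLE supports reimbursement and clinical adoption, and the confirmatory evidence is the double-blind RCT. Longer-treatment questions go to a separate plan and to appendices (OLE SAP 2.1, 7.9.1), where active-active may be analysed. All of that stands. It limits what is at stake but does not make the conclusion in 7.8.2.1 and 7.8.2.2 follow from the test.

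A reader might infer that a blinded concurrent control is being ignored. The documents do not support this. Active-active is on open-label active device in the OLE, and only its RCT allocation is undisclosed. Even that masking may not hold: moving from an unpowered to a powered headset (Protocol 1.1.6) could let passive-active participants infer their earlier arm, and expectation would then differ between the groups.

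A reader might also infer that the bias always favours the device. Regression and an early passive response would mainly work against OLE success; open-label expectation is the component that clearly works for it.

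The figures are open to challenge too. Shifts and correlations are assumed. The SD of 70.8 comes from a cohort with higher Part I scores, and the RCT SAP expects this trial's SD to be lower; a lower SD would raise the rate for any given shift. The MDS-NMS rates and the Part I power are on different scales and should not be compared.

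**Conclusion.** The point holds as a limit on interpretation. Rejection would show that passive-active participants improved more in the open-label active period than in the blinded passive period. It would not show that the device was the cause, so neither the conclusion of success nor that of clinical meaningfulness follows.

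The size is illustrative. With no device effect, favourable shifts of 5, 10 or 15 MDS-NMS points give 11-14%, 20-30% or 32-51% false success, assuming SD 70.8, n = 74 and visit correlation 0.6-0.8. A 1-point Part I shift gives 48% on the plan's own paired inputs. The documents neither measure such a shift nor fix its direction.

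The contrast with active-active helps because it removes effects common to both groups, but it estimates starting versus continuing treatment. It is not strong enough to act as a gate. The RCT's own randomised, double-blind comparison is not affected.

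**What to change.** In both 7.8.2.1 and 7.8.2.2, replace the conclusion of success with: *rejection shows greater within-person improvement in the open-label active period than in the blinded passive period*. Changing only 7.8.2.1 would leave the same inference standing in 7.8.2.2.

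Add a supportive, non-gating estimate with its confidence interval: the day 113-197 change in MDS-NMS in passive-active minus active-active, from the same repeated-measures model with site. Report it beside the primary result wherever the OLE is described as reproducing the RCT.

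The cost is SAP wording and one more contrast on data already scheduled, with no new visits. The SAP should state the drawbacks: the contrast compares starting with continuing treatment; it covers only RCT completers who consent to the OLE; participants may infer their earlier arm; and power falls if active-active keeps improving. The last is plausible, since Protocol 4.3 reports that response had not levelled off at 8 weeks in the single-site study.
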